10.3.5 Analyses for Liver Elevations

According to FDA's Guidance for Industry "Drug-Induced Liver Injury: Premarketing clinical evaluation (July 2009), when aminotransferase (AT) abnormalities indicating hepatocellular injury are accompanied by evidence of impaired hepatic function (bilirubin elevation $> 2 \times \text{ULN}$), in the absence of evidence of biliary obstruction (i.e., significant elevation of ALP) or some other explanation of the injury (e.g., viral hepatitis, alcohol hepatitis), the combined finding (i.e., Hy's Law cases) represents a signal of a potential for the drug to cause severe DILI.

For the purpose of assessing for potential Hy's law cases, the frequencies and percentages of subjects with post baseline liver specific function test values that meet the following criteria of potential clinical interest will be summarized by exposure group:

- $\text{ALT} \geq 3 \times \text{ULN}$
- $\text{ALT} \geq 5 \times \text{ULN}$
- $\text{ALT} \geq 10 \times \text{ULN}$

- ALT $\geq 20 \times$ ULN
- AST $\geq 3 \times$ ULN
- AST $\geq 5 \times$ ULN
- AST $\geq 10 \times$ ULN
- AST $\geq 20 \times$ ULN
- TBL $\geq 2 \times$ ULN
- Alkaline phosphatase $\geq 1.5 \times$ ULN
- ALT and/or AST $\geq 3 \times$ ULN and concurrent TBL $\geq 1.5 \times$ ULN
- ALT and/or AST $\geq 3 \times$ ULN and concurrent TBL $\geq 2 \times$ ULN

A listing of potentially clinically significant liver elevations based on criteria specified above will be provided. For each of these subjects, the whole course of the respective parameter will be listed.

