**Table 3. Clinical Laboratory Tests**

Hematology	Clinical Chemistry	Urinalysis a	Other Laboratory Tests
Hematocrit	Blood Urea Nitrogen (BUN)	Specific gravity	Serum pregnancy Test (Human Chorionic Gonadotropin [HCG]) b
Hemoglobin	Creatinine	Ketones	
Red Blood Cell (RBC) count	Total bilirubin	pH	
White Blood Cell (WBC) count	Serum glutamic-pyruvic transaminase (SGPT/ALT)	Protein	High sensitivity C-reactive protein (hs-CRP)
Neutrophils	Serum glutamic-oxaloacetic transaminase (SGOT/AST)	Blood	FSH c
Bands	Alkaline phosphatase	Glucose	
Lymphocytes	Creatinine Phospho-Kinase (CPK)	Urobilinogen	
Monocytes	Sodium	Bilirubin	
Basophils	Potassium	Microscopic examination, if needed	
Eosinophils	Chloride		
Reticulocytes	Bicarbonate		
Platelet count (estimate not acceptable)	Calcium		
	Inorganic phosphorus		
	Uric acid		
	Cholesterol		
	LDL cholesterol		
	HDL cholesterol		
	Total protein		
	Glucose		
	Triglycerides		
	Albumin		
	INR (reflex only) d		

- a. A dipstick urinalysis will be completed by the central laboratory at all required visits. A microscopic analysis will be performed in the event the dipstick results show protein, ketones or blood greater than negative.
- b. Urine pregnancy test will be done at all scheduled clinic visits and at home between visits. Serum pregnancy test will be done if urine test is positive. Note that pregnancy tests are being performed only for women of childbearing potential.
- c. FSH will be done to confirm post-menopausal status if age of the female is less than 55 years with no menses for 12 or more months without an alternative medical cause AND an FSH level > 40 IU/L.
- d. INR will only be measured with a separate blood sample at repeat testing if ALT and/or AST > 3 × ULN.

For any laboratory test value outside the reference range that the investigator considers to be clinically significant:

- The investigator will repeat the test to verify the out-of-range value.
- The investigator will follow the out-of-range (Clinically Significant) value(s) to a satisfactory clinical resolution.

A laboratory test value(s) that requires a subject to be discontinued from the study or requires a subject to receive treatment will be recorded as an adverse event.

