**Table 5. Specific Toxicity Management Guidelines for Abnormal Laboratory Values (Continued)**

Laboratory Parameter	Toxicity Management Guideline
AST or ALT	
 
• Interrupt study drug immediately if confirmed ALT or AST > 3 × ULN by repeat testing with new sample and either a total bilirubin > 2 × ULN or an international normalized ratio > 1.5.               
 
○ A separate blood sample for INR testing will be needed to measure INR at the time of repeat testing for ALT or AST. A repeat test of INR is not needed for determination if above toxicity management criteria are met.
 
 
 
• Interrupt study drug immediately if confirmed ALT or AST > 3 × ULN by repeat testing with new sample along with appearance of fatigue, nausea, vomiting, right upper quadrant pain or tenderness, fever, rash, and/or eosinophilia (> 5%).
 
• Interrupt study drug immediately if confirmed ALT or AST > 5 × ULN by repeat testing with new sample for more than 2 weeks.
 
• If ALT or AST > 8 × ULN, interrupt study drug immediately, confirm by repeat testing with a new sample and contact the TAMD.
 
 
Subjects who meet any of the above criteria should be evaluated for an alternative etiology of the ALT or AST elevation and managed as medically appropriate. If applicable, the alternative etiology should be documented in the eCRF. If ALT or AST values return to the normal reference range or its Baseline value, study drug may be restarted. If restarting study drug, documentation should include reason that rechallenging is expected to be safe. If after clinically appropriate evaluation, no alternative etiology for ALT or AST elevation is found or the ALT or AST elevation has not resolved or is not trending down toward normal, the subject should be discontinued from study drug
 
 
• For subjects with HBc Ab+ (irrespective of HBs Ab status) and negative HBV DNA at screening who develop the following should have HBV DNA by PCR testing performed within one week:               
 
○ ALT > 5 × ULN OR
 
○ ALT or AST > 3 × ULN if an alternative cause is not readily identified.
 
 
 
• A positive result for HBV DNA PCR testing in these subjects will require immediate interruption of study drug and a hepatologist consultation should occur within one week for recommendation regarding subsequent treatment.
 
 
For any confirmed ALT or AST elevations > 3 ULN, complete supplemental hepatic eCRF.

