**Table 5. Specific Toxicity Management Guidelines for Abnormal Laboratory Values (Continued)**

Laboratory Parameter	Toxicity Management Guideline
AST or ALT	
 
• Interrupt study drug immediately if confirmed ALT or AST <math>> 3 \times</math> ULN by repeat testing with new sample and either a total bilirubin <math>> 2 \times</math> ULN or an international normalized ratio <math>> 1.5</math>.               
 
○ A separate blood sample for INR testing will be needed to measure INR at the time of repeat testing for ALT or AST. A repeat test of INR is not needed for determination if above toxicity management criteria are met.
 
 
 
• Interrupt study drug immediately if confirmed ALT or AST <math>> 3 \times</math> ULN by repeat testing with new sample along with appearance of fatigue, nausea, vomiting, right upper quadrant pain or tenderness, fever, rash, and/or eosinophilia (<math>> 5\%</math>).
 
• Interrupt study drug immediately if confirmed ALT or AST <math>> 5 \times</math> ULN by repeat testing with new sample for more than 2 weeks.
 
• Interrupt study drug immediately if confirmed ALT or AST <math>> 8 \times</math> ULN by repeat testing with new sample.
 
 
Subjects who meet any of the above criteria should be evaluated for an alternative etiology of the ALT or AST elevation and managed as medically appropriate. If applicable, the alternative etiology should be documented in the eCRF. If ALT or AST values return to the normal reference range or its Baseline value, study drug may be restarted. If restarting study drug, documentation should include reason that rechallenge is expected to be safe. If after clinically appropriate evaluation, no alternative etiology for ALT or AST elevation found or the ALT or AST elevation has not resolved or is not trending down toward normal, the subject should be discontinued from study drug.
 
For any confirmed ALT or AST elevations <math>> 3</math> ULN, complete supplemental hepatic eCRF.
 
 
• For Subjects with HBc Ab+ (irrespective of HBs Ab status) and negative HBV DNA at screening who develop the following should have HBV DNA by PCR testing performed within one week:               
 
○ ALT <math>> 5 \times</math> ULN OR
 
○ ALT or AST <math>> 3 \times</math> ULN if an alternative cause is not readily identified.
 
○ A positive result for HBV DNA PCR testing in these subjects will require immediate interruption of study drug and a hepatologist consultation should occur within one week for recommendation regarding subsequent treatment.
 
 
 
 
For any confirmed ALT or AST elevations <math>> 3</math> ULN, complete supplemental hepatic eCRF.

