10.3 Analysis of Laboratory Data

10.3.1 Variables and Units

All laboratory parameters to be collected in this study are listed below. Laboratory parameters will be reported using the standard international (SI) units.

Table 6. List of Laboratory Variables

Laboratory Variables
Hematology
White Blood Cell (WBC) Count
Red Blood Cell (RBC) Count
Hemoglobin
Hematocrit
Platelets count
Neutrophils
Basophils
Eosinophils
Lymphocytes
Monocytes
Reticulocytes
Bands
Chemistry
Total Bilirubin
Alkaline Phosphatase (ALP)
Serum glutamic oxaloacetic transaminase (SGOT/AST)
Serum glutamic pyruvic transaminase (SGPT/ALT)
Total Protein
Albumin
Glucose
Triglycerides
Blood Urea Nitrogen (BUN)
Creatinine
Uric acid

Table 6. List of Laboratory Variables (Continued)

Laboratory Variables
Chemistry (Continued)
Sodium
Potassium
Calcium
Inorganic Phosphorus
Creatine Phosphokinase (CPK)
Chloride
Bicarbonate
Cholesterol
LDL cholesterol
HDL cholesterol
Urinalysis
Specific Gravity
pH
Protein
Glucose
Ketones
Blood
Microscopic Examination
Immunologic Laboratory Assessments
Rheumatoid Factor (RF)
Anti-CCP antibody
Advanced Lipid Panel
Apo A1
Apo B
Other
hSCRp
HBs Ab
HBc Ab
Hbs Ag

Table 6. List of Laboratory Variables (Continued)

Laboratory Variables
Other (Continued)
HBV DNA PCR reflex only
HCV Ab
HCV RNA reflex only
QuantiFERON-TB Gold

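### The SAP's liver table and listing leave out INR, although INR > 1.5 is one of two ways to meet the protocol's combined ALT/AST interruption criterion

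*SAP*

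**What the plan says.** **Protocol.** Section 6.10, Table 5, sets a study-drug interruption trigger. ALT or AST must be above 3 × ULN, confirmed "by repeat testing with new sample and either a total bilirubin" > 2 × "ULN or an international normalized ratio" > 1.5. The UK version in Appendix N has the same rule. INR is collected for it. Table 5 states: "A separate blood sample for INR testing will be needed to measure INR at the time of repeat testing for ALT or AST". Table 3, note d, adds: "INR will only be measured with a separate blood sample at repeat testing if ALT and/or AST > 3 × ULN".

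**SAP.** Section 10.3.1 introduces Table 6 with the words "All laboratory parameters to be collected in this study are listed below". INR is not in that table, although two other reflex tests (HBV DNA PCR and HCV RNA) are. Section 10.3.5 takes its account of Hy's law from FDA guidance and describes impaired hepatic function by bilirubin > 2 × ULN. It then announces the table: "For the purpose of assessing for potential Hy's law cases, the frequencies and percentages of subjects with post baseline liver specific function test values", by exposure group, against a list of criteria. There are twelve:

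- four ALT cut-offs and four AST cut-offs (≥ 3, 5, 10 and 20 × ULN);
- total bilirubin (TBL) ≥ 2 × ULN;
- alkaline phosphatase (ALP) ≥ 1.5 × ULN;
- ALT and/or AST ≥ 3 × ULN with concurrent TBL ≥ 1.5 × ULN;
- ALT and/or AST ≥ 3 × ULN with concurrent TBL ≥ 2 × ULN.

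The liver listing is built from the same criteria and follows each relevant parameter over time.

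**The concern.** The protocol gives raised INR and raised bilirubin the same standing as companions to an ALT/AST elevation, and INR is drawn only for subjects with such an elevation. The SAP section meant to find combined liver signals uses bilirubin alone, and no other SAP section names INR. Followed as written, the plan leaves out of the liver assessment a measurement taken for that assessment.

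Long-term safety is part of the primary objective, and hepatic events are an adverse event of special interest (Protocol section 6.4). Combined liver findings are read case by case, so even one subject who meets the protocol criterion through INR alone should be recognisable in the table or the listing.

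**Working it through.** The documents give no figure to reproduce, so the check runs the two rules side by side.

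**Rules**
- Protocol Table 5: AT > 3 × ULN (confirmed) and (TBL > 2 × ULN or INR > 1.5), where AT is ALT or AST.
- SAP 10.3.5, combined rows: AT ≥ 3 × ULN with TBL ≥ 1.5 × ULN; AT ≥ 3 × ULN with TBL ≥ 2 × ULN.

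**Profiles.** The test values are illustrative assumptions: AT at 4, 6 and 12 × ULN; TBL at 0.8, 1.7 and 2.5 × ULN; INR at 1.0 and 1.8. That gives 3 × 3 × 2 = 18 profiles. The result for the combined rows is the same at each AT level:

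| TBL (× ULN) | INR | Protocol criterion met? | SAP row AT + TBL ≥ 1.5 | SAP row AT + TBL ≥ 2 |
|---|---|---|---|---|
| 0.8 | 1.0 | no | no | no |
| 0.8 | 1.8 | **yes** | no | no |
| 1.7 | 1.0 | no | yes | no |
| 1.7 | 1.8 | **yes** | yes | no |
| 2.5 | 1.0 | yes | yes | yes |
| 2.5 | 1.8 | yes | yes | yes |

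Every profile also falls in the single-parameter ALT (or AST) rows that its AT level reaches: ≥ 3 at 4 × ULN; ≥ 3 and ≥ 5 at 6 × ULN; ≥ 3, ≥ 5 and ≥ 10 at 12 × ULN.

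**Reading the table**
1. Of the 18 profiles, 4 × 3 = 12 meet the protocol criterion. Of these, 2 × 3 = 6 meet it through INR alone (bold).
2. None of those 6 reaches the TBL ≥ 2 row. Three (TBL 1.7) reach the TBL ≥ 1.5 row, but because of bilirubin: the same profile with INR 1.0 is there too.
3. At each TBL below 2 × ULN, the rows for INR 1.0 and INR 1.8 are identical in the SAP columns. The SAP table cannot separate them.
4. With an added row for AT > 3 × ULN and INR > 1.5, all 6 fall in a combined row.

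These are counts of test profiles, not expected subjects. The documents give no INR or liver-event rates, so the number of subjects affected cannot be computed.

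**Listing.** Such a subject is listed under 10.3.5 because of ALT or AST, but INR is neither a criterion nor a listed parameter there.

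**The case against.** The strongest reply is that section 10.3.5 was never meant to tabulate Table 5. Table 5 guides drug interruption. It does not mention Hy's law or define serious liver injury. It also has ALT/AST triggers based on symptoms or eosinophilia, on more than 2 weeks above 5 × ULN, and on values above 8 × ULN, and 10.3.5 reproduces none of them. The SAP states a bilirubin-based definition and tabulates it, with a wider row at 1.5 × ULN. This stands: 10.3.5 is not internally wrong, and the gap is one of alignment between protocol and SAP.

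The second reply is that other outputs may show the subject:
- Protocol section 6.3.1 refers to the toxicity-management criteria when it says which laboratory abnormalities count as adverse events. Such an event would enter the treatment-emergent rates and, depending on the coded term, the hepatic special-interest category.
- Subjects taken off study drug because of an adverse event enter the discontinuation summaries and listing.
- A supplemental hepatic form is completed for confirmed elevations above 3 × ULN.
- SAP section 10.3.4 applies NCI CTC grading to parameters outside OMERACT, which could in principle take in INR.

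This stands in part. The subject need not be lost from the report. But none of these routes joins INR to ALT/AST. The SAP plans no summary of the hepatic form, and section 10.3.4 does not name INR.

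A third reply is that INR can be raised by anticoagulants, which are not among the prohibited therapies in Protocol section 5.2.3.1. This also stands. It calls for a separate row and a visible flag, and is no reason to leave INR out.

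**Conclusion.** The point holds as a protocol–SAP mismatch. INR is collected for a criterion in which it is an alternative to bilirubin, yet it is absent from SAP Table 6 and from the rows and listing of 10.3.5. A subject who qualifies only through INR looks the same in the liver table as one with a normal INR.

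A reader might infer that the SAP under-counts Hy's law cases or severe liver injury. The documents do not support that. The only Hy's law definition in them is the bilirubin one that 10.3.5 applies, the SAP has no severe-liver-injury category to under-count, and Table 5 is an interruption guideline. A reader might also infer that such a subject is always counted purely as a transaminase elevation. That is not so when TBL is 1.5 to < 2 × ULN, or when ALP reaches its own row.

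The size in subjects is unknown and may be zero. The conclusion assumes that reflex INR results reach the analysis database. It is a worthwhile, inexpensive improvement to the safety outputs and takes no position on the clinical rule.

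**What to change.** In the SAP:

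1. Add INR (reflex) to Table 6.
2. Keep the existing bilirubin-based rows of 10.3.5 unchanged.
3. Add two supplementary rows by exposure group: ALT and/or AST > 3 × ULN with INR > 1.5 at the repeat test; and a composite that matches the protocol criterion (confirmed ALT or AST > 3 × ULN with TBL > 2 × ULN or INR > 1.5). One INR result is enough, since Table 5 says: "A repeat test of INR is not needed for determination if above toxicity management criteria are met".
4. In the liver listing, show INR and anticoagulant use beside ALT, AST, TBL and ALP.
5. Define concurrent, which 10.3.5 uses without a time window, for both bilirubin and INR.
6. State that INR exists only for reflex-tested subjects, and give the number with a result.

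The cost is SAP wording, two table rows and added listing columns. It uses laboratory and concomitant-medication data that the protocol already collects, and changes neither the protocol nor any clinical rule. The downside is that INR raised by anticoagulation may enter the new rows. Keeping those rows separate from the bilirubin rows, with the listing beside them, lets a reader see this.

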10.4 Analysis of Vital Signs and Weight

10.4.1 Variables and Criteria Defining Abnormality

Vital sign variables include sitting systolic blood pressure, sitting diastolic blood pressure, pulse, body temperature, and weight. The criteria for potentially clinically significant vital sign findings are presented in [Table 7](#).

Table 7. Criteria for Potentially Clinically Significant Vital Sign Findings

Vital Sign	Category	Criteria for Potential Clinically Significant Vital Signs
Systolic blood pressure	Low	Value ≤ 90 mmHg and decrease ≥ 20 mmHg from Baseline
	High	Value ≥ 160 mmHg and increase ≥ 20 mmHg from Baseline
Diastolic blood pressure	Low	Value ≤ 50 mmHg and decrease ≥ 15 mmHg from Baseline
	High	Value ≥ 105 mmHg and increase ≥ 15 mmHg from Baseline
Weight	High	> 7% increase from baseline
	Low	> 7% decrease from baseline

10.4.2 Analysis of Long-Term Vital Signs

Mean changes from Baseline to post-baseline visits will be summarized with the baseline mean, the visit mean, change from baseline mean, standard deviation, and median. The number and percentage of subjects meeting the criteria for potentially clinically significant vital sign values will be summarized.

A listing of all subjects with any vital sign values meeting the criteria for potentially clinically significant vital signs will be provided. For each of these subjects, the whole course of the respective parameter will be listed.

11.0 Summary of Changes

Version Number	Date	Description of Revision
1.0	15 July 2015	Original Version
2.0	25 October 2016	
This version of SAP includes the changes summarized below:
 
Section 4.2 – Design Diagram
 
 Update the length of study from 96 week to 264 week and the actual number of subjects participating in the study. Update the information on switching to once-daily tablet formulation. 
Section 4.3 (in version 1.0) – Sample Size
 
 Delete the section because it does not provide useful information. 
Section 4.3 – Interim Analysis
 
 Remove the part of the description of efficacy/safety analysis that is no longer applicable to our updated analysis scheme. Change the title to Interim Analysis because the section only contains information on interim analysis. 
Section 5.1 – Open-Label Treated Population
 
 Change the wording for three treatment groups in open-label treated population to make them it clear. Include the information on the use of as randomized open-label treated population for supportive efficacy analysis up to Week 24. 
Section 6.1 – Demographic and Baseline Characteristics
 
 Include information to clarify that baseline is calculated at the baseline visit of the preceding RCT studies. Include geographic region for demographic characteristics. Include duration of prior DMARDs used (for Study M13-537 subjects), number of mechanisms of action for prior biologic DMARD(s) used (for Study M13-550 subjects). 
Section 6.3 – Previous Treatment and Concomitant Medications
 
 Change the definition of prior medication to be any medication taken prior to the first dose of open-label study drug.

Version Number	Date	Description of Revision
		
Section 8.1 – Study Drug exposure
 
 • Change the duration intervals from exclusive to cumulative. • Delete the part for the calculation of study drug exposure based on double-blind and open-label periods combined. 
Section 8.2 – Compliance
 
 • Change the definition of treatment compliance to account for the fact of switching to once-daily formulation. 
Section 9.1 – General Considerations
 
 • Update the analysis scheme to include a long term efficacy analysis as the main analysis, which is based on the open-label treated population. • Update the analysis scheme to include a supportive efficacy analysis up to Week 24, which is based on the as randomized open-label treated population and a subset of most important endpoints. 
Section 9.2 (in Version 1.0) – Exploratory Efficacy Variables
 
 • Delete the section because it is redundant. 
Section 9.2 – Handling of Multiplicity
 
 • Add information to clarify why handling of multiplicity is not needed. 
Section 9.4 – Efficacy Variables Definitions and Conventions
 
 • Include the suggestion of the use of the corresponding programming specification for details on the computation of composite endpoints. • Add a subsection for Joint Evaluation. • Add a subsection for Patient's Global Assessment of Disease Activity Visual Analog Scale (VAS). • Add a subsection for Physician's Global Assessment of Disease Activity Visual Analog Scale (VAS). • Add a subsection for Patient's Global Assessment of Pain. • Add a subsection for Simplified Disease Activity Index (SDAI). • Delete the subsection for SF-36. 
Section 9.4.1 – ACR Criteria
 
 • Remove the detailed instructions for the computation of ACR and relocate them into the programming specification. 
Section 9.4.9 – Low Disease Activity
 
 • Change the Criterion for LDA base on DAS28 (CRP) to be $2.6 \leq \text{DAS28 (CRP)} \leq 3.2$.

Version Number	Date	Description of Revision
		
Section 10 – Safety Analysis
 
 • Remove the language involving statistical testing (i.e., ANCOVA, Fisher's exact test) because it is not meaningful to compare treatment groups in open-label treated population. • Update MedDRA version to 19.0. • Add the phrase "in open-label treated population" in multiple places to clarify the population on which analysis will be performed. 
Section 10.2 – Analysis of Adverse Events
 
 • Remove the part for summarizing SAEs collected between the signing of the informed consent and the first dose. 
Section 10.2.1.1 – Adverse Event Overview
 
 • Delete the description regarding how to handle unknown severity. 
Section 10.2.1.2 – Adverse Events by System Organ Class and Preferred Term
 
 • Update the language according to the current Immunology convention. 
Section 10.2.1.3 – Adverse Events by Maximum Severity
 
 • Change "Select TEAEs" to "TEAEs." 
Section 10.2.1.4 – Adverse Events by Maximum Relationship
 
 • Update the language regarding TEAE summarization to be "TEAEs will be summarized by maximum relationship to ABT-494 only." • Change "probably related or possibly related" to "Reasonable Possibility." 
Section 10.2.1.5 (in version 1.0) – Adverse Events by "Reasonably Possibly Related" Relationship
 
 • Delete the section due to redundancy. 
Section 10.2.1.7 – Adverse Events of Special Interests
 
 • Update the list for summarizing AESI. 
Section 10.2.1.8 – Adverse Events by 100 Patient Years
 
 • Include information on summarizing AESI. 
Section 10.3.2.4 – Potentially Clinically Significant Laboratory Values
 
 • Add NCI CTC criteria for parameters not covered in the OMERACT criteria.

Version Number	Date	Description of Revision
		Section 10.4.1 – Variables and Criteria Defining Abnormality 
 • Update the table "Criteria for Potentially Clinically Significant Vital Sign Findings" according to the current Immunology convention.
3.0	03 May 2021	This version of SAP includes the changes summarized below: Section 3.0 – Introduction 
 • Remove disease background to align with phase 3 standards. Section 4.2 – Overall Study Design and Plan 
 • Update the length of study from 264 weeks to 312 weeks. • Include details of Amendment 5 providing the option to decrease dose to 15 mg QD. • Add clarification that follow-up visit is available after completion of OLE last visit or after PD visit. Section 4.3 – Data Monitoring Committee (DMC) Activities 
 • Include to align with phase 3 standards. Section 5.1 – Analysis Populations 
 • Remove treatment group sequences and relocate to efficacy analysis. • Remove As Randomized Open-Label Treated Population. Section 5.2 – Definition of Baseline 
 • Add clarification that RCT baseline will be used for both efficacy and safety analysis. Section 5.3 – Analysis Windows 
 • Include to align with phase 3 standards. Section 5.3 (in Version 2.0) – Variables Used for Stratification of Randomization 
 • Remove since it is not needed for this study. Section 5.4 (in Version 2.0) – Subgroups Definition 
 • Remove since it is not needed for this study. Section 6.1 – Demographics and Baseline Characteristics 
 • Update to align with phase 3 standards where applicable. Section 6.3 – Prior medication 
 • Update to define prior medication as any medication prior to the first dose of preceding RCT study. • Update language to align with phase 3 standards. Section 6.4 – Protocol Deviations 
 • Include to align with phase 3 standards. Section 7.0 – Patient Disposition

Version Number	Date	Description of Revision
		
 • Add Other category in reasons for discontinuation. 
Section 8.1 – Study Drug Exposure
 
 • Add exposure groups for the Open-Label Treated Population. • Update duration of exposure to utilize exposure group rather than treatment sequence group. 
Section 9.1 – Efficacy Analysis General Considerations
 
 • Remove Supportive Efficacy Analysis Up to Week 24. • Add treatment group sequences relocated from analysis population. 
Section 9.1.1 – Definition of Missing Data Imputation
 
 • Add to describe imputation for MMRM and GLMM models. 
Section 9.2 – Long-Term Efficacy Analysis
 
 • Add to elaborate on long-term efficacy analysis. • Update assessments after Week 96 to occur every 12 weeks to be consistent with data collection. • Add proportion of subjects achieving SDAI criteria as reported measurement. • Add long-term longitudinal analysis performed using MMRM or GLMM performed only for treatment sequences 1 and 2. • Update Table 2 according to above changes. 
Section 9.3 (in Version 2.0) – Efficacy Subgroup Analysis
 
 • Remove since it is not needed for this study. 
Section 9.3.1 – ACR Criteria
 
 • Add definition of ACR20, ACR50, and ACR70 along with illustrated example • Add windowing rule for ACR response calculation. 
Section 9.3.6 – Disease Activity Score Based on CRP (DAS28[CRP])
 
 • Update formula to provide descriptive footnotes. • Add description of Observed DAS28 score calculation. 
Section 9.3.7 – Clinical Disease Activity Index (CDAI)
 
 • Add description of Observed CDAI score calculation. 
Section 9.3.8 – Simplified Disease Activity Index (SDAI)
 
 • Add description of Observed SDAI score calculation. 
Section 9.3.9 – Clinical Remission (CR) and Low Disease Activity (LDA)
 
 • Replace Section 9.4.9 (in Version 2.0) and Section 9.4.10 (in Version 2.0) with table of definitions. 
Section 10.1 – Safety Analysis General Considerations

Version Number	Date	Description of Revision
		
 • Change the AE summary to be presented by the added exposure groups. • Add clarification that the laboratory value analysis will be presented by treatment sequence groups. 
Section 10.2.1 – Adverse Event Rates per 100 Patient-Years
 
 • Change the TEAE summary to be presented by the added exposure groups. • Remove Frequent TEAE categories. 
Section 10.2.1 – Adverse Event Rates per 100 Patient-Years
 
 • Change the TEAE by SOC and MedDRA PT summary to be presented by the added exposure groups. • Redefine Frequent TEAE category to greater-than or equal-to 2 events per 100 patient-years. • Remove Frequent TEAE reasonably possibly related to study drug category. 
Section 10.2.3 (in Version 2.0) – TEAEs by Maximum Severity
 
 • Delete since this is not reported for long-term. 
Section 10.2.4 (in Version 2.0) – TEAEs by Maximum Relationship
 
 • Delete since this is not reported for long-term. 
Section 10.2.3 – Serious Adverse Events and Adverse Events Leading to Study Drug Discontinuation
 
 • Change the SAE, deaths, and adverse events leading to study drug discontinuation summary to be presented by the added exposure groups. 
Section 10.2.4 – Frequent AE by SOC and MedDRA PT
 
 • Redefine Frequent TEAEs to greater-than or equal-to 2 events per 100 patient-years. 
Section 10.2.5 – Safety Analysis General Considerations
 
 • Change the AESI summary to be presented by exposure groups. 
Section 10.3.3 – Assessment of Shift from Baseline in Clinical Laboratory Variables
 
 • Update shift from baseline analysis to align with phase 3 standards where applicable. 
Section 10.5 (in Version 2.0) – Analysis of ECG Parameters
 
 • Delete due to redundancy with baseline characteristics. 
Appendix D – Statistical Analysis to Account for Impact of COVID-19 Pandemic

Version Number	Date	Description of Revision
		
Add detail of additional patient disposition summaries and long-term data handling required to account for impact of COVID-19

